The pharmacist Co-Investigator on the study will devise a randomization code in consultation with [name] (Biostatistician). This code will be kept confidential and will be employed by the pharmacy to dispense the study pills. For each arm, subjects would receive sufficient pills for 7 days of administration. If additional pills are needed to extend the treatment arm by up to three days, these will be dispensed separately by the pharmacy. Subjects will take their study medication at home for days 1 through 6 (+ up to 3 days, if needed). Day 7 (+ up to 3 days, if needed) dosing will be in the clinic. Subjects will be instructed to bring their study medication bottle back to the clinical center for day 7 (+ up to 3 days, if needed) dosing and to not take the day 7 (+ up to 3 days, if needed) dose until instructed to by the study team. If the subject forgets to bring the study bottle with the day 7 (+ up to 3 days, if needed) dose, the day 7 (+ up to 3 days, if needed) dose will be ordered through CRIS from the pharmacy. A process has been developed by the NHLBI pharmacist to ensure the subject receives the correct study compound or placebo. The day 7 (+ up to 3 days, if needed) pill for each arm will be given to the study subject for consumption following the 24-hour fasting research blood draw. The study pill receptacle will have the subject's name, code number, prescription details (4 tablets by mouth each morning with or without food) and will include the arm (1 or 2). If the study subject does not bring in the pill bottle, the subject will be asked to confirm the number of study doses taken over the prior 6 (+ up

Amendment F, May 22, 2018 [name], PhD to 3 days, if needed) days and this will be documented in the medical record. The pill bottles will then either be collected at the next visit or we will have the subject return by FedEx. The code will be shared with the statistician following the completion of studies on 20 subjects to evaluate observed standard deviations to assess original study assumptions and continued study feasibility.

Description of Study Population and Recruitment

Participants will be enrolled at the NIH Clinical Center. Subjects will be recruited through a LISTSERV email announcement and study procedures will be performed in the outpatient unit/day hospital at the NIH Clinical Center. A list of healthy volunteers may also be requested from the NIH Office of Patient Recruitment.

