We propose that NR functions as a fasting mimetic and we will assess whether after refeeding the NLRP3 inflammasome activation (IL-1\beta release) is blunted by NR as the primary endpoint. In our prior study, the mean±SD value of fasting IL-1β release was 319±513 pg/ml, while the mean refed value was 736±1067 pg/ml (with 417±613 pg/ml for the paired refed-fasting IL-1β release differences). In this placebo-controlled crossover study, we would like to detect a relative reduction of at least 20% in refeeding IL-1β release (from 736 to 589 pg/ml) with NR treatment compared to the paired responses on placebo. The crossover design has the benefit of reducing the influence of confounding covariates (because each subject serves as their own control) and is statistically efficient, requiring fewer subjects than non-crossover designs. Since estimates of within-subject variability for both the NR and placebo arms, between-subject variability for the NR arm, and between-subject covariance between NR and placebo are not available for this novel exploratory study, the usual crossover study sample size formulas cannot be used. Instead, we calculate sample size using the paired Student t-test. With a standard deviation of 276 pg/ml (45%) of that observed for the fasting-refed differences), 80% power and an alpha=0.05, we will need 30 subjects to detect a 20% relative decrease (absolute decrease of 147 pg/dl from 736 to 589 pg/dl) for the paired treatment differences in IL-1β release with NR treatment. We therefore request approval to enroll up to 35 normal volunteers to account for possible treatment non-compliance and /or study dropouts.

There will be no interim efficacy look at the data in this proof-of-concept study. However, when 20 subjects have completed the study, the protocol statistician will perform a sample size re-

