calculation using only the observed standard deviation of the paired between treatment IL-1β changes to assess the original study assumptions and continued study feasibility. The study PI will remain blinded to the primary outcomes. The study will be judged feasible jointly by the study PI and Statistician if the new sample size calculation shows that 50 or fewer subjects can answer the primary hypothesis concerning IL-1β. If the study is feasible and continues, the sample size will not be reduced below the originally calculated requirement of 30 but, if needed, a request for a new larger enrollment ceiling (not to exceed 58 subjects, accounting for study drop-outs and non-adherers) will be presented to the IRB for consideration.

Of note, the sample size recalculation was performed on October 19th, 2017 after the enrollment of 20 subjects. The study sample size was recalculated using an updated observed standard deviation of the between treatment fed-fasting differences in IL-1beta levels (S = 177.002 pg/ml) based on 17/20 evaluable subjects enrolled into the protocol. The new calculation was performed for fed-fasting differences rather than fed differences between treatments (a more conservative approach) to allow adjustment for any differences in baseline fasting IL-1beta levels between study periods. With an observed standard deviation of 177 pg/ml, 80% power, and a two-sided alpha=0.05, we will need n=36 subjects to detect a 20% relative decrease (absolute decrease of 83 pg/ml from the protocol-specified mean level of 417 pg/ml to 333 pg/ml) for the paired fed-fasting differences between treatments in IL-1beta release with NR treatment. As the study continues to be feasible (requires the enrollment of fewer than 50 subjects), we request approval to continue enrolling up to 42 normal volunteers to account for possible treatment non-compliance and/or study dropouts.

Primary study outcome:

The primary study outcome will be the refeeding IL-1 β secretion in response to inflammasome stimulation in the NR treatment arm versus the same subject's response on the placebo treatment arm using the nonparametric Wilcoxon Signed Rank test.

Additional Analyses:

- NLRP3 inflammasome activation in PBMC's (IL-1β in the fasting state)
- Isolate PBMC's to explore mitochondrial functioning and biochemistry (oxygen consumption rate in leukocytes)

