- Flow cytometry to explore innate and adaptive cell profiles (assessment of cell surface markers to assay cellular polarity and activation)
- Negative selection to extract T-cells to investigate primary culture T-cell polarity (ELISA assays to measure cytokine production following T-cell activation)
- Serum samples for SomaLogic Proteome analysis and Luminex analysis of cytokine levels (discovery proteomics data collection)
- ELISPOT analysis of T_H1/T_H2/T_H17 cytokine polarity following TCR crosslinking (Alternate assay to measure CD4 T-cell polarity)

In this pilot study, the parametric paired Student t-test and the non-parametric Wilcoxon Signed Rank test will be used to analyze treatment differences in secondary outcome measurements.

11. Stopping Rules for Subjects

- Pregnancy and breastfeeding
- Subjects taking less than 75% of the supplement
- Any other significant medical symptoms that may or not be related to the treatment and as determined by contact with the physician
- Subjects who are found to be pregnant or wish to breastfeed during the study will automatically be withdrawn. A pregnancy screening will be done for all female volunteers at the first visit and subjects will be excluded from the study if pregnant

12. Data and Safety Monitoring

Safety Monitoring

Accrual and safety data will be monitored by the Principal Investigator, [name]. Ph.D., who will provide oversight to the conduct of this study.

Accrual and safety data will be monitored and reviewed annually by the Institutional Review Board (IRB). Prior to implementation of this study, the protocol and the proposed subject informed consent document will be reviewed and approved by the properly constituted IRB operating according to the 45 CFR 46. This committee must approve all amendments to the protocol or informed consent document, and conduct continuing annual review so long as the protocol is open to accrual or follow up of subjects.

Adverse Event Reporting

Adverse Event (AE): Any untoward medical occurrence in a human subject, including any abnormal sign (e.g., abnormal physical exam or laboratory finding), symptom, or disease, temporally associated with the subject's participation in the research, whether or not considered related to the subject's participation in the research.

Abnormal laboratory values: A moderate and severe abnormal laboratory value will be considered an AE if the laboratory abnormality is characterized by any of the following:

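### Must Section 10 name a scale, an effect estimate and an interval alongside the signed-rank test before a 20% fall in refed IL-1β can be judged?

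*Combined protocol and SAP*

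**What the plan says.** Section 10 (Statistical Considerations) states the aim in relative terms: "we would like to detect a relative reduction of at least 20% in refeeding" IL-1β release on NR compared with placebo. It turns this into an "absolute decrease of 147 pg/dl from 736 to 589 pg/dl". The unit there should read pg/ml, as it does for the SD in the same sentence. The prior study supplies the reference level, "while the mean refed value was 736±1067 pg/ml", and the original sample size of 30 comes from a paired t-test with an SD of 276 pg/ml.

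The current size of 36 comes from the October 2017 recalculation. That used fed-minus-fasting differences: a fall of 83 pg/ml (20% of 417) with an observed SD of 177 pg/ml from 17 evaluable subjects.

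The Primary study outcome paragraph then compares refed IL-1β on NR with the "response on the placebo treatment arm using the nonparametric Wilcoxon Signed Rank test". Under Additional Analyses, the paired t-test and the signed-rank test "will be used to analyze treatment differences in secondary outcome measurements". Neither paragraph mentions an effect estimate, a confidence interval or a transformation.

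Section 5 (Randomization and dispensing of study pills) adds: "The code will be shared with the statistician following the completion of studies on 20 subjects". Section 10 limits that look to the standard deviation and keeps the principal investigator blinded to the primary outcomes.

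**The concern.** The target is a size of effect, but the plan names only a test. A p-value alone does not show whether a positive result reached 20%, or whether a null result rules 20% out.

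Two features sharpen the worry. First, the signed-rank test gives different answers on raw and logged data, and the analysis sentence does not say which is meant. A statistician holding the code could in principle choose. Second, the estimate that belongs to the test on raw differences (Hodges-Lehmann) targets a pseudo-median. In right-skewed data with a proportional effect, that lies well below the mean difference of 147 pg/ml used for sizing. A reader who compared the two would take a true 20% fall for something smaller.

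**Working it through.** **1. The plan's own figures.** For a paired design the normal approximation is n = (1.960 + 0.842)² × (SD/δ)², with (1.960 + 0.842)² ≈ 7.85.

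- Original: δ = 0.20 × 736 = 147 and SD = 0.45 × 613 = 276. This gives 7.85 × (276/147)² = 27.7, so 28. With the noncentral t, two-sided 5%, n = 30 (power 80.5%), as stated.
- Recalculated: δ = 83 and SD = 177.002. This gives 7.85 × (177.002/83)² = 35.7, so 36, as stated. The noncentral t gives 38.

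Both calculations are done on untransformed pg/ml.

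**2. Skew.** The ratio SD/mean is 1067/736 = 1.45 for a quantity that cannot be negative, so the distribution has a long right tail. If it is log-normal (an assumption), the log variance is ln(1 + 1.45²) = 1.13 and the median is about 418 pg/ml. The simulated pseudo-median is 521 pg/ml.

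**3. An exact 20% fall in every subject, no noise.**

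| Summary | Value | Percentage fall |
|---|---|---|
| Mean difference | 0.20 × 736 = 147 | 147/736 = 20% |
| Hodges-Lehmann, raw | 0.20 × 521 = 104 | 104/736 = 14%, but 104/521 = 20% |
| Hodges-Lehmann, log scale | ratio 0.80 | 20% |

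The raw estimate looks short only when a pseudo-median is divided by a mean. Against its own kind of reference it gives 20%.

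**4. Noise matched to the planning SD of 276.** This corresponds to a within-subject log SD of 0.107.

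- In a large simulated population the mean difference is still 147 (20% of 736). The raw Hodges-Lehmann value is 94 pg/ml: 94/736 = 13% of the mean and 18% of the placebo pseudo-median. The log-scale ratio is 0.80.
- In trials of 36 subjects the median raw Hodges-Lehmann estimate is 92 pg/ml, and it reaches 147 in about 3% of trials. Across the shapes tried (log-normal, gamma, Weibull) at about this SD, it is 82–111 pg/ml: 82/736 = 11% to 111/736 = 15%.
- In simulated trials of 36 under the same mean, SD and proportional effect (log-normal and gamma), the protocol's own kind of summary, 1 − mean(NR)/mean(placebo), had a median of 19.5–20.1%. The median mean difference was 133–144 pg/ml.

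So the mismatch is real for one particular reading of one unplanned estimate. It is absent for a summary built the way Section 10 states its target.

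**5. Does the unstated scale threaten the test?** Type I error was 4.3–5.2% on either scale taken alone. At SD 276 and n = 36 both versions had power near 100%. In other simulated settings, many of them noisier, raw and log verdicts at 5% disagreed in 0–22% of trials (log-normal) or up to 28% (gamma). Choosing the scale after seeing the data raised type I error to 6.0–7.6%. That inflation requires a deliberate switch. Nothing in the text suggests one: the effect sizes, SDs and prior values for IL-1β in Section 10 are all in concentration units, and no logarithm or ratio transformation appears.

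**The case for a change.** The strongest case for a change is that a pilot earns its value by informing the next trial, and an interval does this better than a p-value. With no NR effect, the median lower 95% limit of the NR/placebo ratio was 0.82–0.95 in 18 of 20 simulated log-normal settings. A null result would therefore often exclude a 20% fall, and the plan does not commit to showing it. Fixing the scale and the estimate would take two or three sentences, and doing so before final unblinding removes a choice from a statistician who may already hold the code.

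It is also fair to say that the shortfall of the raw estimate does not hinge on one shape, since log-normal, gamma and Weibull levels all show it. A constant shift of 147 pg/ml would remove it, but that model fits poorly: under the log-normal, about 16% of placebo values lie below 147 and would turn negative.

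What stands is that reporting an estimate with a 95% interval is good practice here, and that a raw Hodges-Lehmann figure should not be read against 147 or 736. What does not stand is that the plan goes wrong without the addition. Silence about an interval does not prevent reporting one, and an interval by inversion comes with the named test. The log-ratio alternative is not cleaner in every respect. It needs a detection-limit rule that the documents do not supply. Under gamma or Weibull levels it centred on 0.81–0.82, with coverage as low as 89%, although it would be read against 0.80.

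**Conclusion.** No change is called for. The omission is genuine, but it is a gap that analysts fill sensibly. Differences in pg/ml are implied by every sizing calculation, the signed-rank test of no effect is valid on that scale, and no gain in power is claimed for logging. The 20% is the effect the trial was sized to detect in a proof-of-concept study with a directional hypothesis. It is not a threshold on which success is declared.

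The apparent understatement is about 82–111 pg/ml instead of 147 near the planning SD. It arises only if a pseudo-median is added and then compared with a mean. The current 36 subjects rest on 83 pg/ml out of 417 with SD 177 for fed-minus-fasting differences, so 147 is not the figure behind today's sample size in any case.

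The simulated values assume a proportional effect, skewed shapes fitted to the prior study's mean and SD, and chosen noise levels. The documents do not give this trial's own refed distribution. The conclusion that the plan yields a sound test does not depend on those assumptions.

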Additional studies have been initiated or planned using NR to study effects on mitochondrial biology related conditions including aging (at the University of Colorado in Boulder – actively recruiting) and in heart failure (University of Washington in Seattle – protocol in developmental stage). Based on blood levels of NAD⁺ from a pilot study performed at the University of Iowa, the dose of NR chosen by aging and heart failure studies is 1 gram daily. The PI ([name]) has also discussed the experience to date with Drs [name] (UC – Boulder) and [name] (U. of Washington). As of May 17, 2016 the Boulder team has enrolled 20 subjects of whom 10 subjects had been taking 1 gram of NR daily with no evidence of intolerance or side effects. The Seattle team has completed a pharmacokinetics study (NCT02689882) on 8 subjects taking incremental doses up to 1 gram bid up to 9 days. This study revealed no significant side effects and enrollment of the first subject on the heart failure study had been initiated. We therefore propose to use the 1 gram daily dose.

3. Hypothesis

Nicotinamide riboside, as a Sirt3 activator, will mimic the beneficial immune effects of prolonged fasting and suppress immune activation of refeeding.

Proposed Scientific/Clinical Innovations and Advances of the Study

- Evaluate whether pharmacologic activation of Sirt3, via enhancing mitochondrial integrity will blunt sterile-inflammation linked NLRP3 inflammasome activation.
- Expand our understanding how NR can modulate the regulation of additional innate and adaptive immune pathways

[figure not shown]
4. Objectives

- 1. Explore whether NR administration will blunt NLRP3 activation in human subjects.
- 2. Explore whether NR will modulate additional innate (NK cell) and adaptive (T-cell) immune programs.
- 3. Employ proteomic and cytokine array analysis to obtain a broader understanding of the NR mediated effects on mitochondrial biology in modulating immune regulation in circulating cells and in the serum of study subjects.

5. Study Design and Procedures

The study design is a prospective, double-blind randomized crossover study with subjects serving as their own controls.

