Normal volunteers will be enrolled on this 3-5 week study that includes 3 visits to the NIH Clinical Center. Subjects may be contacted by telephone, text or email to verify study compound compliance, for AE/safety assessment and to remind subjects to initiate the 24-hour fast prior to Visit #2 and Visit #3. Email communications will be made through the NIH medical secure email system unless the patient declines its' use and requests standard unsecure email. A schematic showing the outline of the overall study is shown below.

The variable length of the washout and study arms phase is to allow flexibility for the scheduling of subject visits. The prior pharmacokinetic studies support that 7 days is more than sufficient to restore NAD⁺ levels to baseline.

The following actions will be undertaken at the defined visits:

Arm 1

Screening/Visit 1:

- Subjects will be screened for inclusion or exclusion.
- Baseline screening laboratories performed.
- Pregnancy testing in women of childbearing potential.

- Eligible subjects will be randomized to placebo (i.e. sugar tablet) or 1 gram of NR daily. The study compound start date will be determined at this visit. Start date will be within one week of screening visit.
- Instruct subject on study compound administration, reinforce maintenance of stable diet and activity level during the study participation period, and review the time of the breakfast on day 6 (+3 days, if needed), prior to initiating the 24-hour fast.

Day 1 of Arm 1 study compound administration.

A member of the research team may contact study subjects:

- to remind them which day to initiate therapy
- to remind subjects of the 24-hour \pm 2hr fast

Visit 2: Day 7 (+ up to 3 days, if needed) of Arm 1 study compound administration

- Subjects will arrive at the Clinical Center after a 24-hour fast ± 2 hours with the
 exception of drinking water starting the morning of day 6 (+ up to 3 days, if
 needed).
- A pill count will be performed to evaluate compliance.
- Fasting blood draw for hepatic panel, acute care panel, insulin, growth hormone, complete blood count, serum immune cell studies and to measure NAD levels.
- Urine collection for ketones
- Administer day 7 (+ up to 3 days, if needed) Arm 1 placebo/NR capsules.
- A 500 caloric meal will be eaten.
- Refed blood-draw for insulin, growth hormone, glucose, serum immune cell studies and to measure NAD levels three hours ± 30 minutes after fixed caloric meal (metabolic kitchen).

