All tests will follow NIH Clinical Center policies. Any of the listed procedures or laboratory tests performed within three months prior to enrollment in this protocol may/may not be repeated. However, if these procedures are not repeated, the prior studies (within the last 3 months) will be reviewed in CRIS as part of the protocol. The purpose for not repeating study procedures is to prevent unnecessary inconveniences, risks or discomforts for study participants and the NIH Clinical Center.

- *i)* **Blood Draws:** In addition to the screening blood draw (40 mL), subjects will have 4 additional research blood draws up to 100 mL each, as described in Section 4.
- *ii) Urine Analysis:* Subjects will be asked to provide up to three urine samples, one for pregnancy testing as part of screening evaluation and two in the fasting state at Visits 2 and 3 as described in Section 4.
- *iii)* 24-Hour Fasting: Subjects will be asked to fast for up to 26 hours (water intake will not be restricted) during each of the two treatment arms.
- *iv) Fixed Caloric Meal:* The meal will be a 500 calorie breakfast. Subjects will have a choice of two meals.

| Meal Choices | Description of Meal | | | | |
|--------------|---|--|--|--|--|
| Option 1 | Vegetable omelet | | | | |
| | Toast with butter and jelly | | | | |
| | Orange juice | | | | |
| Option 2 - | Oatmeal with Walnuts, Brown Sugar and Dried | | | | |
| | Cranberries | | | | |
| | • Milk | | | | |

8. Dietary Supplement

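### The primary crossover test has no period term; comparing Visit 2 minus Visit 3 between the two randomised orders would guard against a period shift for about 1 point of power

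*Combined protocol and SAP*

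**What the plan says.** Section 5 describes a "prospective, double-blind randomized crossover study with subjects serving as their own controls". Treatment in the first period is randomised at Visit 1: "Eligible subjects will be randomized to placebo (i.e. sugar tablet) or 1 gram of NR daily". The other treatment follows after a washout of 7 to 14 days. There are therefore two orders, NR then placebo and placebo then NR, and refed IL-1β is measured once in each period, at Visit 2 and at Visit 3.

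On allocation, Section 5 (Randomization and dispensing of study pills) says "The pharmacist Co-Investigator on the study will devise a randomization code" with the biostatistician. It gives no allocation ratio and no blocking.

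Section 10 (Primary study outcome) compares refed IL-1β on NR with the same subject's placebo value "using the nonparametric Wilcoxon Signed Rank test". Secondary outcomes use the paired t-test and the signed-rank test. No analysis has a period or sequence term. The sample-size recalculation moved to fed-minus-fasting differences so that differences in fasting IL-1β between periods could be adjusted for, but the primary outcome remains the refed value.

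**The concern.** Let τ be the NR effect and G the shift in refed IL-1β from Visit 2 to Visit 3 that has nothing to do with treatment. The NR minus placebo difference has mean τ − G in subjects who take NR first and τ + G in those who take placebo first. Pooling the two groups has two consequences.

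- With equal group sizes G cancels from the mean but remains as extra spread. The test becomes conservative and less efficient than one that removes G.
- With unequal evaluable groups G does not cancel. The mean difference is biased in proportion to the imbalance.

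A shift is possible because the visits do not occur under identical conditions. Visit 3 always follows an earlier 24-hour fast, and it follows up to 240 ml of blood drawn: 40 ml at screening plus two of the draws in Section 7, where "subjects will have 4 additional research blood draws up to 100 mL each". Equal evaluable groups are not assured either. No balance rule is stated, and only 17 of the first 20 subjects were evaluable.

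**Working it through.** **The plan's own sample sizes**

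- Recalculation (Section 10): "With an observed standard deviation of 177 pg/ml, 80% power, and a two-sided alpha=0.05, we will need n=36 subjects", for a difference of 83 pg/ml. The normal approximation gives (177 × (1.960 + 0.842) / 83)² = 35.7, so 36. The figure reproduces. An exact paired t calculation gives 38.
- Original: SD 276 and "absolute decrease of 147 pg/dl from 736 to 589 pg/dl" (read as pg/ml, the unit used elsewhere in that paragraph). The exact paired t calculation gives 30, with power 80.5%. The figure reproduces.

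**Inputs for the comparison**

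- Effect 147 pg/ml and SD 276 pg/ml: the planning values for the refed endpoint. The updated SD of 177 belongs to fed-minus-fasting differences, and no updated refed SD is given.
- n = 36 evaluable, two-sided alpha 0.05.
- Assumptions not in the documents: normal differences, and a shift G of 0 to 1 SD of the NR minus placebo difference.
- Simulation: at least 40,000 trials per scenario, exact critical values for both tests.

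**The adjusted test.** Take Visit 2 minus Visit 3 for each subject. Its mean is τ − G in the NR-first order and −τ − G in the placebo-first order. The difference between the orders is 2τ; G has gone. A Wilcoxon rank-sum test between orders therefore tests τ, and half the shift between orders estimates it.

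**Power at 18:18.** If 276 contains no period variance, the pooled SD grows to 276 × √(1 + s²), where s = G/SD; at s = 0.5 it is 309. If 276 already contains it, the SD within each order is 276 / √(1 + s²); at s = 0.5 it is 247.

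| Shift (SD) | 276 free of period variance: signed-rank | adjusted | 276 includes it: signed-rank | adjusted |
|---|---|---|---|---|
| 0 | 86% | 85% | 86% | 85% |
| 0.25 | 84% | 85% | 86% | 87% |
| 0.5 | 79% | 85% | 88% | 92% |
| 0.75 | 70% | 85% | 90% | 96% |
| 1 | 56% | 85% | 91% | 99% |

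Under the first reading, signed-rank type I error at 0.5 SD is 2.9%.

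**Unequal orders, shift 0.5 SD (138 pg/ml).** The bias is G × (n1 − n2) / N. At 20:16 it is 138 × 4 / 36 = 15.3 pg/ml, and 15.3 / 147 is about 10% of the target effect. Signed-rank power is 69% or 87%, depending on the direction of the shift, against 85% adjusted. Signed-rank type I error, given the split, is 3.7% at 20:16, 6.5% at 22:14 and 11.8% at 24:12. The adjusted test stays between 4.6% and 5.0%.

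**How likely such splits are**

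- 21:21 enrolled with 6 random losses (hypergeometric): 20:16 or worse has probability 18%, and 21:15 is the worst possible split.
- Simple randomisation of 36 (binomial): 20:16 or worse 62%, 22:14 or worse 24%, 24:12 or worse 7%. Averaged over all splits, signed-rank type I error at 0.5 SD is 4.9%.

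**Price of adjusting when there is no shift.** About 1 point at 18:18 or 20:16, 2 to 3 at 22:14 and 5 at 24:12. At n = 30 (15:15) it is about 2 points.

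**Sensitivity**

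- Heavier tails (t with 4 df, SD 276), 18:18, 0.5 SD: 88% signed-rank against 93% adjusted.
- Recalculation inputs (83.4 and 177, n = 36, 18:18): signed-rank 77%, 75%, 68% and 42% at 0, 0.25, 0.5 and 1 SD, against 75% adjusted. This treats 177 as free of period variance.

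**The case against.** The strongest case for leaving the test alone has four parts.

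- **No shift is documented.** The remark in Section 10 about fasting levels between periods is precautionary, and a washout separates the periods. Under equal orders the planned test is valid, and averaged over simple randomisation its type I error is nominal. If allocation is 21:21 with 6 losses, the splits that inflate it cannot occur. This stands, and it is why the point concerns efficiency and robustness.
- **Planned power may not fall.** The observed SD of 177 probably already contains any period variance. This also stands: under that reading there is no shortfall, only forgone efficiency (88% against 92% at 0.5 SD).
- **IL-1β is skewed.** Section 10 gives a refed mean of 736 with SD 1067. In lognormal simulations with a 20% NR effect, a 10% period shift brought no gain from adjusting, and a shift of 147 pg/ml brought about 2 to 5 points. But in those data 147 pg/ml is only about 0.27 to 0.37 SD. A shift of 221 pg/ml, about 0.4 to 0.55 SD, brought 7 to 8 points, no less than under the normal model. Skewness does not remove the gain.
- **The change comes late.** The statistician received the code after 20 subjects, and an amendment needs IRB approval. This affects timing: the change must be fixed before the final treatment comparison. It is not a reason to omit it.

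**Conclusion.** The point holds as an inexpensive improvement that should be made; it does not invalidate the planned test. At 18:18, once a shift reaches about 0.25 SD the adjusted test is at least as powerful under either reading of the planning SD. At 0.5 SD it gains 4 to 6 points, and at 20:16 with an unfavourable shift it gains about 16 (85% against 69%). Inflated type I error needs both a real shift and a split of about 22:14 or worse. Confidence is medium, because neither the shift nor the evaluable split is known from the documents and the main figures assume normal differences. The adjustment removes an additive period effect; it does not deal with carryover.

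**What to change.** In Section 10, make the primary test a Wilcoxon rank-sum comparison, between the two randomised orders, of each subject's Visit 2 minus Visit 3 refed IL-1β. Report half the Hodges-Lehmann shift with its 95% confidence interval, and keep the signed-rank test as a sensitivity analysis. In Section 5, state the allocation ratio and any blocking, and report the number evaluable in each order. Make the change before the final treatment comparison.

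The cost is one or two sentences in Section 10, a line on allocation and the IRB review that any amendment requires. It needs no new data, visits or subjects; the power given up if there is no period shift is set out in the working.
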